1. AMENDMENT HISTORY

Amendment No.	Protocol Version No.	Date issued	Author(s) of changes	Details of Changes made
0	1.1	28 October 2014	[name]	Additional information about screening under study procedures
1	1.2		[name]	Addition of cognitive assessment approach to children with very severe disability.
2	1.3	23 Sept 2015	[name]	Adding option of assessment at home or school for children with severe mobility problems or for those that have emigrated to other countries.

2. SYNOPSIS

Study Title	Surgical drainage, irrigation and fibrinolytic therapy (DRIFT) in premature infants with post-haemorrhagic ventricular dilatation: Brain function and structure at school age
Internal ref. no.	2287
Study Design	Long term follow up of a multi-centre randomised controlled trial
Study Participants	Participants of the DRIFT Trial
Planned Sample Size	60
Follow-up duration	
Planned Study Period	01/09/2014 to 31/05/2016
Primary Objective	To compare cognitive function, visual function, sensorimotor ability and emotional well-being between the two treatment groups form the DRIFT trial, at school age
Primary Endpoint	Severe cognitive disability at school age
Intervention (s)	None

3. BACKGROUND AND RATIONALE

3.1 Summary Background and Rationale

3.1.1 Lay Summary:

Despite advances in newborn intensive care, infants born prematurely are at high risk of brain injury and major disabilities/neurodevelopmental impairments later in life. Bleeding into the fluid spaces (ventricles) of the brain is one of the most common consequences of being born very early. These bleeds, called Intraventricular Haemorrhage (IVH) are often further complicated by progressive enlargement of the ventricles, known as post–haemorrhagic ventricular dilatation (PHVD), which has a very high rate of serious disability such as cerebral palsy and learning difficulties.

Despite a number of different approaches to therapy, no intervention has been objectively shown to improve outcome. Drainage, irrigation and fibrinolytic therapy (DRIFT) was developed as a method of washing out the ventricles to clear the effects of the bleeding. The DRIFT randomised trial was conducted in 2003-2006. Eligible babies were preterm, had an IVH and expanded the cerebral ventricles over pre-determined limits. With parental consent, 54 babies were randomised in Bristol and a further 20 in Poland, to either DRIFT or standard therapy which consisted of fluid tapping to control excessive expansion.

Magnetic resonance (MR) brain imaging was carried out in 36 babies in the DRIFT trial and showed cerebral lesions and/or impaired brain growth in a large proportion of the infants. When neurodevelopment was assessed by "blinded" observers at 2 years, severe disability or death was significantly reduced in the DRIFT group. There was a large reduction in severe learning difficulties from 59% to 31% in the DRIFT group compared to the control group.

As cognitive testing at 2 years is limited and can be difficult in children with motor impairment, it is important to do more comprehensive testing at school age. Cerebral visual impairment concerns how the brain processes images and cannot be adequately tested at 2 years. Thus it is important to thoroughly assess vision including techniques that can detect and define cerebral visual impairment.

The children in the DRIFT trial are a unique study group with well-documented serious brain injury substantially different from the previous studies of preterm infants, most of whom have not had severe brain injury of this nature. The proposed MR imaging, visual assessment and cognitive assessment at school age will allow us to assess to what extent the brain has remodelled and adapted to the previous injury and will enable us to see if some functions (i.e. vision or language) have "moved" from their normal locations. This study may provide vital insights into how the brain repairs and adapts after injury from IVH in premature infants, enabling future refinement of treatments. The proposed research might ultimately lead to a reduction in disabilities in children born prematurely, with a long-term cost saving to health and education services, and improved quality of life.

In 2012, the investigators tested the feasibility of this protocol in a small group of children from the DRIFT trial. Ethical approval for this research was given by South West 3 Research Ethics Committee, and the study demonstrated that the children (now aged 7-10 years) coped extremely well and were able to cooperate with all the assessments and brain imaging undertaken.

3.1.2 Scientific Summary:

Background:

Haemorrhage into the ventricles of the brain is one of the most common and serious consequences of being born preterm, despite improvements in the survival of preterm infants. Large intraventricular haemorrhage (IVH) is often further complicated by progressive enlargement of the ventricles, post–haemorrhagic ventricular dilatation (PHVD), which has a

very high rate of serious disability, i.e. cerebral palsy and cognitive disability. In the neonatal Research Network 33% of infants with birth weights less than 1000g developed IVH, and of those 10% required implantation of a ventriculoperitoneal shunt for PVHD [1]. 40% of children with PVHD will develop cerebral palsy and approximately 25% of these will have multiple disabilities. The presence of haemorrhagic parenchymal infarction, in addition to PVHD, increases the risk of cerebral palsy to 80-90% [1].

The immature brain may be injured in a number of different ways in PHVD, including pressure, distortion, inflammation and free radical injury from iron [2].

Reducing the rate of shunt insertion in these infants has been an important long-term objective in the management of IVH and PVHD. The large amount of blood and protein in the cerebrospinal fluid (CSF) combined with the small size and instability of the patient makes early ventriculoperitoneal shunt surgery impossible. Shunt implantation at the generally accepted weight threshold of 2kg, usually around term-age, is still associated with a higher infection and malfunction rate [3] [4].

Despite a number of different approaches to therapy, no intervention has been objectively shown to improve outcome. Repeated lumbar puncture, drugs to reduce cerebrospinal fluid (CSF) production and intraventricular injection of streptokinase have been tested in randomised trials with either no benefit or worse outcome in the intervention group.

Drainage, irrigation and fibrinolytic therapy (DRIFT) was developed as a surgical approach of reducing iron and pro-inflammatory cytokines from CSF and reducing pressure and distortion early [2]. The procedure involves insertion of right frontal and left occipital ventricular catheters under anaesthesia. Tissue plasminogen activator (TPA), a fibrinolytic, is injected intraventricularly at a dose that is insufficient to produce a systemic effect and this is left for approximately 8 hours. Under continuous intracranial pressure monitoring the ventricles are irrigated by artificial CSF through the frontal catheter. The occipital ventricular catheter is simultaneously connected to a sterile closed ventricular drainage system and the height of the drainage reservoir adjusted to increase or decrease drainage to maintain intracranial pressure below 7 mm Hg and net loss of 60–100 ml CSF/day. The drainage fluid initially looks like cola but gradually clears, at which point irrigation is stopped and the catheters removed. This commonly takes 72 hours but can be up to 7 days.

After initial feasibility testing showed DRIFT was technically possible and promising, the DRIFT randomised trial started recruiting in 2003. Eligible babies were preterm, had an IVH and expanded the cerebral ventricles over pre-determined limits. With parental consent, 74 babies were randomised in Bristol and Katowice, Poland to either DRIFT or to standard therapy which consisted of non-surgical conventional management (lumbar punctures to control excessive expansion and pressure symptoms). If repeated lumbar punctures were needed, a ventricular reservoir was inserted to facilitate tapping CSF.

Short term outcomes in the DRIFT trial showed no difference in shunt surgery or death. There was a significant increase in secondary bleeding in the DRIFT group. Magnetic resonance (MR) imaging was carried out on clinical indications in 36 of the 50 Bristol survivors.

At 2 years post term, severe disability or death was significantly reduced in the DRIFT group, when neurodevelopment was assessed by "blinded" observers [2]. There was an important decrease in severe cognitive disability (Bayley mental development index 3 SDs below mean) from 59% to 31% (adjusted odds ratio: 0.17 [95% CI 0.05-0.57]) and the difference in median MDI was more than 18 points. Developmental quotient at 2 years correlated significantly with qualitative grading of MR brain images at term. Sensorimotor disability remained substantial at 2 years: overall, 48% were unable to walk, and 20% were unable to communicate. Ventricular enlargement is typically greatest in the occipital areas and 9% of the children had no useful vision. Severe sensorimotor disability was less common in the DRIFT group but without reaching statistical significance.

However, while (relatively) short term neurodevelopmental measures are essential in the initial management of perinatal interventions, longer term measures provide far greater validity in assessing long term functioning (and the medical, societal and financial implications of these).

Prematurely-born children have a higher prevalence of visual defects than do children born at term [5] and in particular the spectrum of vision problems known collectively as "cerebral visual impairment" (CVI) is a recognised complication of preterm brain injury, particularly if involving the periventricular white matter [6]. Visual functions correlate with neurodevelopmental outcome and brain volume in preterm infants [7]. Severe CVI is the leading cause for children being registered as blind in the UK [8] and developed world and may additionally be associated with ocular, optic nerve or refractive problems which cause further impairment. Less severe CVI can involve damage to visual skills which have an important effect on school performance and tasks of everyday life [9]. Clinical assessment of CVI is difficult before the age of 5 years, however a recent study found evidence of CVI in 89% of children with known central nervous system damage [10] thus it is important to assess this area of function to fully understand the impact of severe IVH, PHVD and/or the impact of DRIFT.

Every preterm infant with severe cerebral palsy or severe cognitive or visual impairment will require lifelong parental and social care. The cost to society due to the complications of prematurity is significant. Based on 2003 US figures [11] the estimated lifetime costs per infant with cerebral palsy, severe cognitive impairment and blindness is £614,000, £675,000 and £400,000 respectively. Data from the UK EPICure study indicate that by age 11 the annual health and social service costs of children with serious neurodevelopmental disability are almost double those of children without disability (£1,225 vs £695) [12]. This adds a significant additional economic burden on the NHS and social care.

As cognitive testing at 2 years is limited and can be difficult in children with motor impairment, it is important to do more comprehensive testing at school age. Cerebral visual impairment concerns more complicated aspects of vision than just visual acuity or strabismus and cannot be adequately tested at 2 years. Thus it is important to thoroughly assess vision including techniques that can detect and define cerebral visual impairment. The MR imaging performed at term showed cerebral lesions and/or impaired brain growth in a large proportion of the infants.

The number of new cases of PHVD annually is estimated to be in the region of 200. With increasing rates of premature birth and survival of extremely preterm infants the prevalence of PHVD and severe disability is likely to increase in the future. If the cognitive improvement seen with DRIFT at 2 years translates into a similar effect size at school-age, we can project that serious disability could be prevented in at least 60 infants per year. The projected annual cost saving to the NHS and social services will be about £600,000 per year, based on the additional cost of severe disability [13]. This estimation excludes the further substantial reduction in the economic burden of parents/carers, special educational services and public funds. The impact on individual quality of life and acquisition of independence would also be substantial.

The children in the DRIFT trial are a unique study group with well-documented serious brain injury substantially different from the previous studies of preterm infants, most of whom have not had severe brain injury of this nature. There is now the opportunity and facility for long term (late primary school age i.e. 8-11 years old) to assess cognitive and visual function, functional status, emotional wellbeing, preference based measures of health related quality of life and healthcare costs of the DRIFT trial participants to determine further evidence of clinical efficacy, safety and cost-effectiveness of DRIFT therapy. Two year developmental outcomes are important, but often limited to detecting substantial neurodevelopmental impacts and have limited role in measurement of functional outcomes. With an invasive technique such as DRIFT

it will be important to quantify any benefit or risk of the procedure in comparison to conservative treatment.

The children in the DRIFT trial have now reached the age where cognitive and visual abilities and functional impact on activities of daily living can be assessed definitively and where the children will be able to cooperate with neuroimaging, even in the presence of disabilities. The feasibility of conducting this research protocol has been tested in Bristol. Children from the DRIFT trial were successfully recruited and completed the required assessments and imaging studies and coped well during their participation.

4. AIMS AND OBJECTIVES

Our primary hypothesis is that neurosurgical drainage, irrigation, and fibrinolytic therapy (DRIFT), which aims to lower pressure, distortion, free iron, and cytokines, will reduce severe cognitive disability in children assessed at school age.

Our secondary hypotheses are that DRIFT will improve:

- (a) cerebral visual dysfunction
- (b) sensorimotor ability
- (c) functional status
- (d) emotional/behavioural difficulties
- (e) preference based measures of health related quality of life
- (f) and reduce the health, social care and broader societal costs at age 11.

The aims of this study:

- 1) To compare cognitive function, visual function, sensorimotor ability and emotional wellbeing, between the two treatment groups in the DRIFT trial at school age.
- 2) To quantify functional status and use of community and specialist health and educational services.
- 3) To estimate the economic cost and outcomes of the DRIFT intervention by age 11, and model long-term costs and outcomes.
- 4) To quantify degree of ventricular dilatation and neurosurgical sequelae in the two treatment groups by clinical neuroimaging.

4.1 Primary Outcome

Severe cognitive disability at school age.

4.2 Secondary Outcomes

- Cerebral visual function
- Sensorimotor disability
- Functional status
- Emotional/behavioural function
- Preference based measures of health related quality of life
- Costs of initial hospitalisation and treatment during the neonatal period (including emergency transportation, periods of intensive care, and readmissions based on hospital records in the UK cohort)
- Costs of subsequent health care in childhood (based on hospital records from the UK cohort)
- Health and social care costs and impact on family at age 11 (based on parent recall)

5. STUDY DESIGN

Study design: Long term follow up of a multicentre randomised controlled trial

5.1 Study Participants

Children previously enrolled in and randomised to the DRIFT trial in Bristol and Poland between 2003 and 2006.

Inclusion criteria of the DRIFT trial were:

- (1) IVH documented on ultrasound;
- (2) age no more than 28 days;
- (3) progressive dilation of the both lateral ventricles with each side:
 - (a) ventricular width 4 mm over the 97th centile;

(b) all of the following: anterior horn diagonal width 4 mm (1 mm over 97th centile), thalamo-occipital distance 26 mm (1 mm over 97th centile), and third ventricle width 3 mm (1 mm over 97th centile); or

(c) measurements above (a) or (b) on 1 side combined with obvious midline shift indicating a pressure effect.

Exclusion criteria were a prothrombin time of >20 seconds or accelerated partial thromboplastin time of >50 seconds or platelets <50000/mL.

The DRIFT study achieved a high level of loyalty from those recruited as 100% followup was obtained at 2 years with 97% of the survivors having the full Bayley Scales of Infant Development administered. All the families received a copy of the paper reporting the two year findings of the trial. The families with a child in the DRIFT trial will be invited to take part.

5.2 Statistical Considerations

In total 74 children (54 from Bristol and 20 from Poland) were randomised to the DRIFT trial of which 66 survived. 16 children are available for assessment in Poland and 50 in Bristol. Based on a similar effect size documented with severe cognitive disability at 2 years of age a two group continuity corrected chi-square test with a 5% two-sided significance level will have 80% power to detect the difference in severe cognitive disability between a control group proportion of 59% and odds ratio of 0.17 (i.e. an intervention proportion of 19.7%) when the sample size in each group is 28. With 60 infants (30 in each group) we will have 97% power (with an alpha of 5%) to detect a mean cognitive difference of 1 standard deviation (commonly 15 points) between the DRIFT and control groups.

45 UK children will be assessed in Bristol, and 15 Polish children in Katowice, Poland, assuming a 90% follow-up rate. It is intended to recruit 45 Children (22 DRIFT, 23 Control) from the Bristol cohort and 15 (8 DRIFT, 7 Control) from the Poland cohort.

Funding is available for the study to be completed in the UK and in Poland. **This protocol describes the UK cohort only**. The Poland cohort will be completed under a separate protocol and in accordance with local governance and regulatory requirements.

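### Section 5.2 states 80% power for an unadjusted chi-square by applying the adjusted odds ratio of 0.17 to the 59% control rate; for the 59% vs 31% reported at 2 years, that test has about 44-50% power

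*Protocol*

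**What the plan says.** The sample size paragraph in section 5.2 opens: "Based on a similar effect size documented with severe cognitive disability at 2 years of age". It names the test as "a two group continuity corrected chi-square test with a 5% two-sided significance level" and says that it "will have 80% power to detect the difference in severe cognitive disability", taking "a control group proportion of 59% and odds ratio of 0.17 (i.e. an intervention proportion of 19.7" per cent, "when the sample size in each group is 28". It does not say that the odds ratio is an adjusted one.

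The 2-year result itself is in section 3.1.2, where severe cognitive disability fell "from 59% to 31% (adjusted odds ratio: 0.17 [95% CI 0.05-0.57". The lay summary (3.1.1) gives the same two rates: "severe learning difficulties from 59% to 31% in the DRIFT group compared to the control group".

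Section 5.2 plans for 60 children, 30 per group, out of 66 survivors. It adds a second power statement: 97% for a difference of 1 standard deviation in mean cognitive score.

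**The concern.** A two-group chi-square test compares the overall proportions in the two arms. The planning value for the DRIFT arm should therefore be an overall proportion, and the one the protocol reports at 2 years is 31%. Section 5.2 instead takes an odds ratio estimated after covariate adjustment and applies it to an overall control rate. An adjusted odds ratio is conditional on the covariates and does not convert into an overall proportion in this way. The result, 19.7%, is about 11 points below the reported 31%. The planned difference becomes 39 points (59 − 19.7 = 39.3) where the reported one is 28 (59 − 31).

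What is at stake is how the binary comparison is read. The synopsis and section 4.1 name severe cognitive disability as the primary endpoint, and the primary hypothesis in section 4 is framed on it. The 80% figure is the only power given for that endpoint. Someone relying on it would think this test very likely to detect the 2-year difference if it were fully maintained, when for those rates the chance is about one in two.

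**Working it through.** **Inputs.** From section 5.2: two-sided 5% (z = 1.96), 80% power (z = 0.8416), the "two group continuity corrected chi-square test", control rate p1 = 0.59, odds ratio 0.17, 28 per group for the power statement and 30 per group as planned. From section 3.1.2: 59% and 31% at 2 years, with 0.17 given as the adjusted odds ratio.

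**1. The DRIFT rate in section 5.2.** Control odds 0.59/0.41 = 1.439. Times 0.17 = 0.2446. Rate = 0.2446/1.2446 = 0.1966, so 19.7% is reproduced.

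**2. The stated sample size and power.** With d = p1 − p2 and p̄ the mean of the two rates:

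- Without correction, m = [1.96·√(2p̄(1−p̄)) + 0.8416·√(p1(1−p1)+p2(1−p2))]² / d². With p2 = 0.1966, d = 0.3934 and p̄ = 0.3933: m = (1.3540 + 0.5322)²/0.3934² = 22.98, i.e. 23.
- With the continuity correction, n = (m/4)·[1 + √(1 + 4/(m·d))]² = 27.8, i.e. 28 per group. Reproduced.
- Power at a given n: m = (n − 1/d)²/n, then Φ{[d√m − 1.96·√(2p̄(1−p̄))] / √(p1(1−p1)+p2(1−p2))}. At n = 28: m = 23.15, and Φ[(1.8930 − 1.3540)/0.6323] = Φ(0.852) = 80.3%. Exact enumeration of the corrected test gives 79.6%. Reproduced.

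**3. The odds ratio implied by the reported rates.** (0.31/0.69)/(0.59/0.41) = 0.449/1.439 = 0.31, not 0.17.

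**4. The same test at 59% vs 31%.** d = 0.28, p̄ = 0.45, 1.96·√(2·0.45·0.55) = 1.3790, √(0.2419 + 0.2139) = 0.6751.

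- n = 28: m = (28 − 3.571)²/28 = 21.31; Φ[(1.2926 − 1.3790)/0.6751] = Φ(−0.128) = 44.9%.
- n = 30: m = (30 − 3.571)²/30 = 23.28; Φ[(1.3511 − 1.3790)/0.6751] = Φ(−0.041) = 48.4%.

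| Power, 59% vs 31% | 28 per group | 30 per group |
|---|---|---|
| Corrected chi-square, formula | 44.9% | 48.4% |
| Corrected chi-square, exact enumeration | 43.6% | 49.6% |
| Fisher's exact test | 44.5% | 49.6% |
| Uncorrected chi-square, formula | 56.0% | 59.1% |
| Uncorrected chi-square, exact enumeration | 55.1% | 60.1% |

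**5. Sample size for 80% at 59% vs 31%.** The formulas in step 2 give m = 48.36 and n = 55.3, i.e. 56 per group or 112 children. Only 66 survive, so this shows the scale of the shortfall and is not a recruitment target.

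**6. The 97% for means.** For a 1 SD difference with 30 per group, the noncentrality is 1/√(2/30) = 3.87 on 58 degrees of freedom, giving 96.8% (97.2% by the normal approximation). Reproduced, and independent of the steps above.

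**The case against.** The strongest reply is that nothing in section 5.2 is miscalculated. It prints its assumptions openly, and 0.17 is an effect size documented at 2 years. That stands as far as it goes: 19.7%, 28 and 80% all follow from the inputs. A reader might also infer that the protocol presents 19.7% as the rate observed at 2 years. It does not; it derives that figure from the odds ratio and reports 31% elsewhere. The fault is narrower. An adjusted odds ratio is paired with an overall rate and an unadjusted test, and the adjustment goes unmentioned where the number is used.

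A second reply is that section 7.4 analyses the primary outcome as a continuous cognitive score with an unpaired t-test, and names the chi-square or Fisher test only for binary secondary outcomes. This limits the consequence. A reader might infer that the whole follow-up has only an even chance of detecting a maintained benefit, or that any null result would be misread as fading of the 2-year effect. The documents do not support that, because the comparison of means has its own power statement, which is correct for its stated 1 SD difference. The 80% still needs correcting, because the endpoint named as primary is the binary one.

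A third reply is that covariate adjustment would recover the lost power. Section 7.4 does foresee a sensitivity analysis adjusting for the original trial's pre-randomisation covariates, but by linear regression; it specifies no adjusted logistic analysis of severe disability. How much power such an analysis would have cannot be worked out from the protocol, which gives neither the covariates' strength nor their balance between arms. Strong covariates and chance imbalance among 74 infants could each open a gap between 0.31 and 0.17, with different implications for power. A claim that adjustment brings power back to about 80% would therefore be unsupported.

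**Conclusion.** The point holds for the binary severe-disability comparison. The 80% in section 5.2 is conditional on a DRIFT rate of 19.7%, which is more favourable than the 31% reported at 2 years. For 59% vs 31% the named test has about 44-45% power at 28 per group and 48-50% at 30 per group, so the stated figure is at least 30 percentage points too high for those rates. Dropping the continuity correction raises power only to 55-60%.

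This rests on two assumptions. The first is that the school-age rates would equal the 2-year rates, which is one reading of the similar effect that section 5.2 invokes. The second is that 59% and 31% are unadjusted rates. The protocol does not label them so, but they imply 0.31 and not the adjusted 0.17, which fits that reading. The 97% power for a 1 SD difference in means is not in question.

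**What to change.** Rewrite the power paragraph in section 5.2 to say three things:

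- 80% power at 28 per group holds only if the true DRIFT rate is 19.7%. This is an assumption, derived from an adjusted odds ratio, and is more favourable than the 31% reported at 2 years.
- For 59% vs 31% with 30 per group, the continuity-corrected chi-square has about 50% power.
- The 97% figure applies to the comparison of mean scores and stands separately.

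If 0.17 is to remain the target effect, pair it with a prespecified covariate-adjusted logistic analysis of severe cognitive disability. Give any power for that analysis as a range under stated assumptions about the covariates.

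The cost is one paragraph and a less favourable stated power, plus the specification of one model if the adjusted target is kept. The cohort is fixed, so neither enrolment nor the assessments change.

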6.1 Cognitive Assessments

Assessment will be undertaken by child psychologists.

Cognitive testing in this group of children needs to use a method with a wide spread of abilities as some of the study children have very significant disabilities (Cognitive score below 55). The British Ability Scales (BAS III) comprise 21 short tests, each measuring particular types of knowledge, thinking and/or skills (Elliott and Smith. GL Assessment; London. 2012). The final type of score is "age equivalent". This is the age at which the score achieved by the child was average. The BAS III has a basal threshold at a developmental age of 3 years. In the event that children do not attain the basal scoring threshold of the BAS III, the cognitive and language scales from the Bayley Scales of Infant and Toddler Development III (BSID III) (Bayley N. Harcourt Assessment: San Antonio; 2006) will be administered. This test also yields Developmental Age Equivalent score from 1 month to 3 years. In order to compare scores in all children, developmental age scores will be converted into a developmental quotient score: [developmental age equivalent score \div biological age at assessment x 100] for each child. This allows severely delayed children to have a cognitive score rather than being labelled as "untestable".[14] The final cognitive score for children of all abilities will therefore be a cognitive developmental quotient and a continuous variable.

The BAS_III and BSID III will be adapted for use in Polish speaking children.

The individual scales for BASIII are:

- Block building
- Copying
- Early number concepts
- Matching letter-like forms
- Matrices
- Naming Vocabulary
- Number Skills
- Pattern Construction
- Picture Construction
- Picture Similarities
- Quantitative Reasoning
- Recall of Designs
- Recall of Digits Backwards
- Recall of objects

- Recognition of pictures
- Speed of information processing
- Spelling
- Verbal Comprehension
- Verbal Similarities
- Word definitions
- Word reading

The individual scales for BSID III are:

- Cognitive Scale
- Language Scale (receptive and expressive language)

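### The 97% power is right for a 1 SD difference, but equating 1 SD with 15 points rests on a test-norm SD that the protocol's own 2-year figures do not support

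*Protocol*

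**What the plan says.** Section 5.2 of the protocol gives two power statements. The first concerns the binary outcome and needs 28 per group. The second concerns mean cognitive scores: "With 60 infants (30 in each group") there is "97% power (with an alpha of 5%) to detect a mean cognitive difference of 1 standard deviation (commonly 15 points") between the two groups. No SD observed in these children is given; the only link between SD units and points is the parenthesis.

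Section 7.4 (Data Analysis) treats the cognitive score as the primary outcome and compares means by an unpaired Student t-test, so the second statement is the one that bears on that test.

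Section 6.1 defines the score. BAS III is used, or Bayley III for children below the BAS III floor, and "developmental age scores will be converted into a developmental quotient score": age equivalent divided by actual age, times 100. The same section says the method must cover a wide spread of abilities, because some of the children score below 55.

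Section 3.1.2 reports the 2-year results of the same trial. Severe cognitive disability (Bayley mental development index, MDI, 3 SDs below the mean) was found in 59% of controls and 31% of the DRIFT group, and "the difference in median MDI was more than 18 points".

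**The concern.** Fifteen points is the SD of a standardised test score in a norming population. The outcome here is a ratio quotient, not a norm-standardised score, in children who range from very severe delay upwards. Nothing in the protocol supports a within-group SD of 15 for that quotient in this cohort, and the 2-year results point to a larger one.

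If the SD exceeds 15, a 15-point difference is less than 1 SD and the 97% does not apply to it. What is at stake is interpretation. A reader of section 5.2 would conclude that the study has only about a 3% chance of missing a 15-point benefit, and could read a non-significant t-test as good evidence against a benefit of that size.

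**Working it through.** **Inputs.** From section 5.2: 30 per group, alpha 5%, difference 1 SD, stated power 97%. The chi-square calculation there is described as "a two group continuity corrected chi-square test with a 5% two-sided significance level"; sidedness is not restated for the means, so two-sided is assumed. From section 7.4: unpaired t-test. From section 3.1.2: 59% and 31% below the 3-SD cut-off, median difference more than 18 points.

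**Step 1. Reproduce the stated figure.** For standardised difference d = difference / SD, the t-test has noncentrality d × √(30/2) on 58 degrees of freedom. With d = 15/15 = 1, power is 96.8% (noncentral t) or 97.2% (normal approximation). The stated 97% is reproduced. A one-sided test would give 98.5%, so two-sided is the better match.

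**Step 2. Check SD 15 against the 2-year results.** Take two normal distributions with a common SD and one cut-off. The gap between their centres is [z(0.59) − z(0.31)] × SD = (0.2275 + 0.4959) × SD = 0.7234 × SD.

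- With SD 15 the gap would be 0.7234 × 15 = 10.9 points, but the protocol reports more than 18.
- A gap of 18 needs SD = 18 / 0.7234 = 24.9. A gap of 19 needs 26.3, and 20 needs 27.6.

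**Step 3. Vary the model.**

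- Unequal SDs: normal scores require 0.2275 × SD(control) + 0.4959 × SD(DRIFT) = 18. The pair with the smallest root-mean-square SD is about 13.8 and 30.0, with root-mean-square 23.3. Power for 15 points is then about 69%.
- Logistic in place of normal scores: SD about 28, power about 53%.
- The 19.7% in section 5.2 in place of 31%: z(0.59) − z(0.197) is about 1.08, SD = 18 / 1.08, about 16.7, power about 93%.

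**Step 4. Power for 15 points, 30 per group, two-sided 5% (noncentral t).**

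| Within-group SD | d = 15/SD | Power |
|---|---|---|
| 15 | 1.00 | 97% |
| 18 | 0.83 | 89% |
| 20 | 0.75 | 81% |
| 22 | 0.68 | 74% |
| 25 | 0.60 | 63% |
| 30 | 0.50 | 48% |

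The difference detectable with 80% power is d = 0.736, about 0.74 SD. In points that is 0.736 × 15 = 11.0 at SD 15, 0.736 × 20 = 14.7 at SD 20 and 0.736 × 25 = 18.4 at SD 25.

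**Step 5. How precise is the inferred SD?** The 2-year denominators are not stated, so assume 33 per arm (66 survivors / 2). In simulated normal samples with a true gap of 15 or 18 points, the Step 2 method returns 24.9 or more in about 2 to 4% of samples if the true SD is 15, about 10 to 12% if it is 18, and about 20% if it is 20. SD 15 looks too low, but 18 to 20 cannot be excluded.

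**The case against.** The sponsor can fairly say that the target is set in SD units, that the power for 1 SD is right whatever the SD turns out to be, and that the parenthesis only recalls a test convention. The first two points stand: a reader might infer a mistake in the power calculation, and there is none. The third does not dispose of the matter, because the parenthesis is the only thing that tells the reader how many points the 97% refers to.

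A second objection is that SD 25 is not a figure in the protocol. It needs normal scores, a common SD and a mean shift equal to the median difference. It comes from small groups, at 2 years, on the MDI, whereas the outcome is a school-age quotient from other instruments. Normality is doubtful in exactly the low range where the cut-off lies. This stands, and it limits the claim. A reader might infer that the study's power for 15 points is 63%; the documents do not establish that, since SDs of 18 to 20, with 89% to 81% power, remain plausible.

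A third objection is that 59% with 19.7% gives an SD near 16.7 and 93% power. That pairing is less coherent: 19.7% is derived from the adjusted odds ratio of 0.17, while 31% is the proportion reported beside the median gap. Even so, it falls short of 97%.

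Finally, the cohort is limited to 66 survivors, so no power figure can change recruitment. That is true, and it is why the point concerns a stated property of the study, not its design.

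**Conclusion.** Wrong as written: an unsupported SD stands behind a stated power. It is not an arithmetic error. The 97% holds for 1 SD; it holds for 15 points only if the within-group SD is 15.

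The 2-year figures do not fit that SD and point to roughly 25 under normal scores with a common SD. Letting the SDs differ between arms, or using a logistic shape, does not bring back 15. The size of the overstatement is uncertain: power for 15 points runs from about 89% to 48% over SDs of 18 to 30, against the 97% stated.

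Two stronger readings are not supported. The documents do not fix the SD at 25 or the power at 63%, and they give no ground for saying that the sample size must be changed.

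**What to change.** In section 5.2, delete the parenthesis equating 1 SD with 15 points and state the power in SD units: with 30 per group and a two-sided 5% test, 97% for a difference of 1 SD and 80% for about 0.74 SD.

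If a figure in points is wanted, compute the within-group SD from this cohort's own 2-year scores, which are already held (section 5.1 says 97% of survivors had the full Bayley assessment). Say that it comes from another age and scale, and show power for 15 points over a range of SDs, for example 18 to 30. Neither 25 nor 63% should be written in as the value.

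The cost is one sentence, or a sentence and a short table. The stated power becomes less favourable. Sample size, design and analysis are unchanged.
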